## 4.1.3 EMG Measurements

(20 minutes)

The Modified Ashworth Scale (MAS) (11) evaluates the resistance to passive movement about a joint with varying degrees of velocity. The MAS is designed to evaluate spasticity. For this task the investigator will extend the participant's hand first from a position of maximal possible flexion to maximal possible extension. Afterwards, the investigator will flex the participant's hand first from a position of maximal possible extension to maximal possible flexion. Both of these motions will be repeated twice for each of the affected upper limbs.

Activity of the muscles due to be involved in BTX-A treatment and surrounding muscles will be observed during these motions using a Trigno wireless surface EMG system (Delsys, Natick, MA, USA).Wireless sensors will be placed on the skin of the participants using adhesive stickers. The participants will be instructed to inform the researcher prior to signing the consent form if they have any allergies or skin conditions. They have also been instructed that if they notice any drying irritation from the sensor adhesive during or immediately following the study, that they should inform the researcher and a clinician assist them. Ultrasound will be used to identify the muscles involved in the participant's BTX-A treatment and surface EMG sensors will be placed on said muscles to record muscle activity.

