## 3.1 Inclusion Criteria

- 1. Participants must be aged between 4 and 18 years.
- 2. Participants must be diagnosed with spastic cerebral palsy in at least one of their upper limbs.
- 3. Participants must be due to start BTX-A treatment for their affected upper limb.
- 4. Participants must have minimum ability to hold an object and stabilise it for use by the other hand.
- 5. Participants must be able to comprehend and complete the test protocol.
- 6. Participant or the participants parent/carer must be able to speak, read and understand English, in order to be involved in this study.

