## Dynamic Positional Analysis (DPA):

The dynamic positional analysis score for each of the tasks is related to joint and limb segment movement. The DPA documents the dynamic, segmental alignment of the extremity when performing the task. The DPA assesses the following five functional/anatomical segments:

Thumb segment alignment:

- Thumb in palm Any combination of metacarpophalangeal joint (MCP) flexion or interphalangeal joint (IP) flexion resulting in the thumb being placed beneath the fingers, in the palm. No visible web space is seen, from any angle at the first web space.
- Thumb Web Space Closed No visible space at the first web space. Thumb is adducted and may have a hyperextended IP joint, but does not cross index metacarpal into palm. No visible web space is seen, from any angle at the first web space.
- Thumb Web Space Open Thumb MCP in abduction. Any visible web space constitutes an "open" score. Participant able to extend or abduct thumb to grasp object. Participant does not have to maintain abducted posture to be given this score.

Finger Segment Alignment

Fingers are graded as a group because they frequently move in composite flexion or extension. The tasks used for thumb evaluation are used for finger evaluation.

- Flexion MCP maintained in greater than 45° flexion. Fingers are held in palm, in variable flexion pattern at DIP joints.
- Neutral Fingers are held in midrange with adequate alignment for task. Fingers easily fluctuate between flexion and extension patterns with no joint aberrations.
- Extension Fingers are held in hyperextension at MCP or IP joints. Associated swan neck deformities or extensor splaying may also be present.

Wrist Segment Alignment

- Flexion Wrist is held in flexed position throughout task; with or without ulnar deviation; any measurement between 0° 80° of flexion.
- Anatomical neutral Wrist in anatomical neutral position of 0° for all or portion of task; with or without ulnar deviation.
- Extension Wrist extends past anatomical neutral position for all or portion of the task; any measurement between 0° 70° of extension.
- Ulnar deviation Wrist is held in an ulnarly deviated position throughout task; any measurement between 0° 30°.
- Neutral Wrist is in the neutral plane; within 5° of neutral.
- Radial deviation Wrist is held in a radial deviated position throughout task; any measurement between 0° - 20°

Forearm Segment Alignment

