- Extreme pronation Excessive pronation, no active supination, resulting in palm away from body; any measurement 91° or greater.
- Pronation Pronated at rest with no active supination during task, resulting in palm to floor; any measurement 0° 90°.
- Neutral Active movement from pronated position to neutral, resulting in 0° palm towards body.
- Supination Active movement beyond neutral to supination with palm open to face. Anything 0° 90°.

Elbow Segment Alignment

- Extreme flexion Participant is unable to actively extend past 90°.
- Flexion Participant is unable to extend past 30°.
- Extension Participant is able to extend between 30° and 0°.

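### The passive-stretch test moves only the hand, so an injected muscle that does not cross the wrist or fingers is recorded by EMG but never stretched

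*Protocol*

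**What the plan says.** Protocol section 4.1.3 describes the Modified Ashworth Scale (MAS) as a test that "evaluates the resistance to passive movement about a joint with varying degrees of velocity". It then fixes two motions. In the first, "the investigator will extend the participant's hand first from a position of maximal possible flexion to maximal possible extension". In the second, "the investigator will flex the participant's hand first from a position of maximal possible extension to maximal possible flexion". On their number it says: "Both of these motions will be repeated twice for each of the affected upper limbs". No other joint is named.

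The EMG recording is tied to those motions: "Activity of the muscles due to be involved in BTX-A treatment and surrounding muscles will be observed during these motions". Ultrasound is used to locate the treated muscles so that the sensors sit over them.

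The treated muscles are not specified. Section 3.1 requires only this: "Participants must be due to start BTX-A treatment for their affected upper limb". Section 4.1 applies the same procedures at all three sessions, one before treatment and two after.

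**The concern.** Within section 4.1.3 the sensors follow the injected muscle but the stretch does not. By the protocol's own description, the MAS informs on the joint that is moved. If a child is injected in a muscle that does not span that joint, the test neither loads nor lengthens it. The recording would then show little or nothing before treatment and little or nothing after. That could be read as an absence of effect when the muscle was never challenged.

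The first session precedes treatment. A stretch response that was not elicited then cannot be recovered later. MAS with EMG is also the only spasticity test the protocol describes, so no other measurement would fill the gap for that muscle.

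The motion is a procedure that the protocol fixes. It is not an analysis detail that would normally be left to a statistical analysis plan.

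**Working it through.** The protocol gives no figure to reproduce on this point. The check sets the relevant sections side by side.

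1. **Segment moved.** Section 4.1.3: the hand, in two directions, with two repeats per affected limb. The word does not settle whether the wrist, the fingers or both are moved.
2. **Muscles recorded.** Section 4.1.3: the muscles to be injected, whichever they are, and their neighbours, during the hand motions only.
3. **Muscles that may be injected.** Section 3.1: any in the affected upper limb. Nothing restricts treatment to wrist or finger muscles.
4. **Any adaptation elsewhere.** None. No section adds a passive elbow or forearm movement to this task or lets the motion depend on the injected muscle.
5. **Contrast with elastography.** Section 4.1.2 measures the tendons at both ends of each muscle scheduled for injection, at rest and under stretch, and repeats this for every treated muscle. That measurement adapts to the child; the MAS/EMG test does not.

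Taking items 1 to 3 together, an injected muscle falls into one of three groups:

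| Injected muscle | Lengthened by passive hand motion? | Stretch-evoked reading |
|---|---|---|
| Crosses the wrist or fingers only | Yes, if the hand motion covers that joint | Obtained |
| Crosses the wrist or fingers and also acts at the elbow or forearm | Yes, through its wrist or finger action | Obtained |
| Crosses neither the wrist nor the fingers | No | Not obtained |

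Only the third group is affected. For those muscles the sensor may still pick up incidental co-activation, but not a response to stretch.

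**Size.** Let k be the number of children, out of the 8 in section 3.4, with at least one injected muscle in the third group. The protocol gives nothing from which to fix k, so it may lie anywhere from 0 to 8. A share of children is also not a share of data. As an illustration only, a child injected in one muscle that crosses the wrist and one that does not loses 1 of 2 = 50% of the injected-muscle readings, not all of them.

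**Time available for a change.** Section 4.1 allows about 1 hour per session. The nine SHUEE tasks at 1 minute each, plus 20 minutes of ultrasound and 20 minutes of EMG, give 9 + 20 + 20 = 49 minutes. One 3-minute rest after each of the three main activities adds 3 × 3 = 9, giving 49 + 9 = 58 minutes before consent and set-up. On that reading about 60 − 58 = 2 minutes are left.

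**Outcomes touched.** Section 4.4 lists tendon elasticity and muscle anthropometrics as primary and the comparison of computational models as secondary. Neither MAS nor EMG appears there, and section 2 states no spasticity objective.

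**The case against.** The reading of section 4.1.3 is hard to dispute, but its reach and consequence can be argued down.

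- **It may never arise.** Children are invited by their hand surgeon (section 3.5), must be able to hold and stabilise an object (section 3.1), and are assessed with hand assessments (section 1). The injected muscles may all cross the wrist or fingers. This stands: the protocol permits other injections but does not show that they will occur.
- **No listed outcome depends on it.** This stands too. A reader might infer that the flaw dilutes a treatment comparison in a sample of 8. The protocol commits to no pooled spasticity analysis, so that does not follow.
- **The elbow scoring proves little.** The SHUEE positional analysis does look beyond the hand ("The DPA assesses the following five functional/anatomical segments"), with an elbow category worded "Participant is unable to actively extend past 90" degrees. But the segments belong to a fixed published instrument, and that item concerns active movement during tasks. It shows that the elbow and forearm are observed, not that they are injected. The argument rests on the eligibility criterion instead.
- **Some elbow and forearm muscles are stretched.** A reader might infer that every injected muscle acting at the elbow or forearm gives no signal. That is too broad, because those that also cross the wrist or fingers are lengthened.
- **Time is short and the children are young.** Ages start at 4, fatigue is a stated concern (sections 4.1 and 5.2), and the hour is almost full. This is a real cost, though it falls only on children whose injected muscles need a different or additional joint moved.

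None of this removes the mismatch between what is recorded and what is moved.

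**Conclusion.** The point holds in a limited form. Followed as written, section 4.1.3 leaves any injected muscle that crosses neither the wrist nor the fingers unstretched at baseline and at both later sessions. For that muscle, resistance and stretch-evoked EMG are not measured, and a finding of no change would be uninterpretable.

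The size is unknown and may be nil. It would be tempting to assume that 2 to 4 of the 8 children are affected and to conclude that 25% to 50% of the MAS/EMG data are lost (2/8 = 25%, 4/8 = 50%). The protocol does not support that. It gives no count of such children, and the step from children to data holds only if each of them is injected solely in muscles of this kind.

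The consequence is confined to a supporting measurement. The primary outcomes in section 4.4 are not compromised by it. The correction is still worth making before the first session, because the baseline cannot be repeated after treatment. The conclusion rests on two assumptions: that hand motion means wrist motion, finger motion or both, and that the eligibility criterion is applied as broadly as it is worded.

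**What to change.** In section 4.1.3, replace the fixed hand movement with passive movement at the joint or joints crossed by each injected muscle. Where the hand is still the segment tested, say whether the wrist, the fingers or both are moved. Keep the two repeats in each direction. Use the same joint and movement for a given child at all three sessions, and record which joint was tested so that the readings can be matched.

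This is a short rewording and needs no new equipment. The cost is a few extra minutes in a session that is already close to its hour, and only for children injected in muscles acting at a different or additional joint. The stated session length should be checked against that. For a child whose injected muscles all cross the wrist or fingers, the procedure stays essentially as it is.

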# 4. Study Design

## 4.1 Methodology

Participants will be asked to take part in all the tests listed below. This will take approximately 1 hour in total. The participants will attend three sessions at the 1st Floor, Paediatric Outpatients, Chelsea and Westminster Hospital ([name]). The first session being before they start BTX-A treatment, the second session will be between 3 weeks and 6 months after treatment and the third session will be at least 6 months after treatment. All the sessions will consist of the procedures described in sections 4.1.1, 4.1.2 and 4.1.3.

Upon arrival at the 1st Floor, Paediatric Outpatients Department, participants' carers will be asked to review the participant information sheet and sign the consent form, if they have not already done so. If the participant is over the age of 16 years of age, they will be asked to sign a consent form. For participants under the age of 16, they will sign an assent form. Demographic information regarding the participant's age (current year and month), diagnosis and any significant birth history or previous surgery will be documented. Participants must consent to the clinical care team

reviewing the ultrasound scan reports to ensure any incidental findings can be appropriately investigated and acted upon.

A camera with a tripod, will be used to video record future data processing. The participant will be seated at a table and the camera will be focused on the participant's upper extremity and the tabletop. For the best observation of participant's extremity, long hair will be restrained, if possible, and their sleeves will be rolled up above the elbow. The participant will be positioned sideways to the camera with uninvolved side closest to the camera and the involved side furthest from the camera. This position allows best visibility of the involved hand and thumb for the video.

Participants will be asked to take part in a series of three main activities: Shriners hospital upper extremity evaluation, ultrasound measurements and EMG measurements. Following each task, a 3-minute rest period will be designated in order to avoid the effects of fatigue.

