## Grasp and Release Analysis (GRA):

The GRA documents if the participant can or cannot grasp and release the object with the wrist in the three different positions. A yes (Y) or no (N) for grasp and release is provided contingent on the participants ability to close and open fingers with the wrist

maintained in each position. Video examples of optimal grasp and release for each position are available online.

The SWE images obtained will be processed using a custom software developed in MATLAB (The MathWorks, Natick, MA, USA) to process the images semiautomatically.

The EMG signals obtained will be processed using a custom software developed in MATLAB that will ensure the signal is low-pass filtered for noise, full wave rectified and smoothed.

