## 4.3 Equipment

A camera will be used to video record for future data processing.

For the SHUEE activity, the following will be used to obtain the corresponding SHUEE scores:

- Billfold style wallet to hold paper money
- 8 x 10 sheet of standard weight paper
- Three American dollar sized bills made of standard weight paper
- Four plastic coins of any size
- One wide-mouth clear 2-2 /2" diameter bottle with 2-2 /2" screw cap
- One Play-Doh® can
- Stickers of any size or type One 30" ball

For the ultrasound measurements, the following devices will be used:

- LOGIQ E10 Ultrasound R2 system (GE Healthcare, Chicago, IL, USA)
- A ML6-15-D probe (GE Healthcare, Chicago, IL, USA)
- Ultrasound gel

The equipment required for the tremor tests includes two triaxial accelerometer sensors (Delsys Trigno).

- Trigno wireless EMG system (Delsys, Natick, MA, USA)
- LOGIQ E10 Ultrasound R2 system (GE Healthcare, Chicago, IL, USA)
- A ML6-15-D probe (GE Healthcare, Chicago, IL, USA)
- Ultrasound gel

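### The passive stretch runs to whatever range the wrist allows that day and the angle is not captured, so a change in range after BTX-A can bias the before/after EMG comparison (minor)

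*Protocol*

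**What the plan says.** Section 4.1.3 introduces the Modified Ashworth Scale as a test that "evaluates the resistance to passive movement about a joint with varying degrees of velocity". The manoeuvre itself is fixed only by its end points. The investigator will "extend the participant's hand first from a position of maximal possible flexion to maximal possible extension", and afterwards "flex the participant's hand first from a position of maximal possible extension to maximal possible flexion". On repetition it says: "Both of these motions will be repeated twice for each of the affected upper limbs". Activity of the muscles due for injection and "surrounding muscles will be observed during these motions using a Trigno wireless surface EMG system". No angle, arc or speed is set.

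Section 4.1 applies this at every visit, before treatment and twice after it: "All the sessions will consist of the procedures described in sections 4.1.1, 4.1.2 and 4.1.3".

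Section 4.2 describes EMG processing as signal conditioning only: the signal is "low-pass filtered for noise, full wave rectified and smoothed". It has no step that relates the signal to joint angle or range.

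Section 4.3 lists no goniometer. It does list "two triaxial accelerometer sensors (Delsys Trigno" model), but assigns them to tremor tests that the methods sections do not describe. It also lists a video camera.

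Section 4.4 names tendon elasticity and muscle anthropometrics as primary outcomes and a comparison of computational models as the secondary outcome. EMG is not named.

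**The concern.** The stretch is the stimulus and the EMG is the response. A before/after comparison of the response is clean only if the stimulus is the same each time, or is known each time. Here it is neither: the arc is whatever can be reached on the day.

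The introduction describes spastic CP as hypertonia that holds the limb in abnormal positions, and BTX-A as a means of reducing spasticity. A change in reachable range between sessions is therefore a plausible result of treatment, although the protocol does not say that it occurs. If it does occur, the stimulus moves with treatment, and the resulting error is a bias that repetition will not average out. A wider arc after injection could add signal and so work against seeing a fall. Holding the stretch speed constant would not remove this.

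At stake is the interpretation of the EMG data. They take 20 minutes of a session of about one hour, three times per child, in a study whose stated sample size is 8.

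**Working it through.** The protocol states no figure on this point, so there is nothing to reproduce. The check has two parts.

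**1. Is the angle fixed or captured anywhere?**

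- Section 4.1.3: end points are the day's limits; only EMG is measured during the motion.
- Section 4.2, SHUEE scoring: wrist and forearm alignment are graded, but during active tasks and not during the passive stretch.
- Section 4.2, EMG processing: filter, rectify, smooth; no reference to angle.
- Section 4.3: no goniometer; the accelerometers are assigned to another test.
- Sections 4.1 and 4.3, video: the upper limb is filmed for later processing, with the involved side furthest from the camera. No section plans to read passive range from the film.

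The protocol therefore does not provide for recording the range, though some of it might be recoverable from video.

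**2. Can a change in range mask a fall in response?**

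All values here are assumptions; none comes from the protocol. Let R be the excursion and g the response per unit of stretch (the gain). Suppose amplitude grows in proportion to excursion at constant speed. Then peak EMG = g × R, and EMG summed over the stretch is proportional to g × R². If R widens by a fraction w and g falls by a fraction d:

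- peak ratio = (1 − d)(1 + w), with break-even at d = 1 − 1/(1 + w)
- summed ratio = (1 − d)(1 + w)², with break-even at d = 1 − 1/(1 + w)²

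| Range widens by | Fall in gain hidden, peak EMG | Fall in gain hidden, summed EMG |
|---|---|---|
| 10% | 1 − 1/1.10 = 9.1% | 1 − 1/1.21 = 17.4% |
| 25% | 1 − 1/1.25 = 20.0% | 1 − 1/1.5625 = 36.0% |
| 50% | 1 − 1/1.50 = 33.3% | 1 − 1/2.25 = 55.6% |

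Two cases show that either direction is possible:

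- Range +25%, gain −10%: peak 0.90 × 1.25 = 1.125 (+12.5%); summed 0.90 × 1.5625 = 1.406 (+40.6%). EMG rises although the response per unit of stretch fell.
- Range +10%, gain −30%: peak 0.70 × 1.10 = 0.770 (−23.0%); summed 0.70 × 1.21 = 0.847 (−15.3%). EMG falls, but by less than the 30% fall in gain.

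**Sensitivity to the model.** Suppose instead that activity per degree is constant, speed is equal, and the arc goes from 80 to 100 degrees (assumed):

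- Sum over the whole arc: 100/80 = 1.25.
- Mean over the arc: unchanged, ratio 1.0.
- Sum beyond a fixed onset at 60 degrees: (100 − 60)/(80 − 60) = 2.0.
- Sum beyond an onset that moves from 60 to 80 degrees with the range: (100 − 80)/(80 − 60) = 1.0.

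The artefact thus ranges from none to a doubling, depending on the summary measure and on where activity starts. The protocol settles neither.

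**The case against.** The strongest reply is that the protocol never says EMG from different arcs will be compared as like for like. It says activity will be observed and gives signal conditioning; it defines no EMG summary and, beyond the generic tests in section 7, no EMG comparison. The choice of measure and analysis window can properly sit in an analysis plan, and some measures, such as a mean over the arc, may be little affected. EMG is also not a listed outcome. This stands, and it limits the weight of the point. It does not remove it, because capturing the angle is data collection: an analysis plan cannot restrict EMG to a common arc if no angle was captured.

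Three stronger readings are tempting, and the documents do not support them.

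- *EMG will rise, or the treatment effect will be reversed.* The protocol has no data on passive range after BTX-A and does not say where in the stretch activity arises. The second case above shows EMG falling despite a wider range.
- *The inflation is two-fold or so.* That needs an onset angle held fixed while the range widens. If the onset moves with the range, the ratio is 1.0.
- *The range is lost altogether.* Video exists and might yield it; what is missing is any plan to do so.

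**Conclusion.** The point holds as a minor one. The protocol fixes the passive stretch by end points that may change with treatment and does not provide for recording the angle reached, so a before/after EMG comparison can be biased in a way that may mask a fall.

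This rests on one assumption: that reachable range changes between sessions as spasticity changes. That is plausible from the introduction but not stated there. The size is unknown; the figures above show only that masking is possible. Stretch speed is also neither set nor recorded, which adds to the same difficulty.

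A reader might infer that the main results are compromised. They are not: section 4.4 does not list EMG among the primary or secondary outcomes, and no section names it as an input to the computational models.

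**What to change.** **Section 4.1.3.** Record the wrist angle at both ends of every passive motion at every session. Also capture a motion signal synchronised with the EMG, for example from the Trigno accelerometers already listed in section 4.3 if they are suitable. End angles alone cannot show which part of the EMG trace lies within a given arc, particularly as speed is not fixed.

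**Section 4.2.** Compare EMG within the arc common to the sessions that each child attended, or as a function of angle, and report passive range alongside. Defining the arc by sessions attended keeps the rule usable for a child who withdraws early, which section 3.3 allows.

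**If no synchronised signal is available.** Report the end angles and interpret the EMG change together with the change in range.

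**Cost.** A few minutes of set-up and processing per session. EMG outside the common arc is left out of the comparison.
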